#### 8 STUDY DESIGN

# 8.1 Overall Study Design

This is a Phase 3b, multicenter, double-blind, parallel group, randomized study that will evaluate the efficacy and safety of 2 treatment regimens of edaravone for a period of 48 weeks in subjects with ALS as follows:

- Group 1: Oral edaravone 105 mg administered once daily for 28 days, in Cycles 1 through 12
- Group 2: Oral edaravone 105 mg administered for 14 days, followed by placebo for 14 days in Cycle 1. Subsequently, repeat oral edaravone 105 mg administered for 10 days followed by placebo for 18 days (regimen denoted as on/off) in Cycles 2 through 12

Eligible subjects will be randomized at baseline in a 1:1 ratio to receive 1 of 2 treatment groups. Randomization will be stratified according to ALSFRS-R rate of decline score for the 8-week screening period (2 levels strata of -1,-2 or -3,-4) and geographical region (3 levels strata of Europe, North America, or Asia Pacific).

This study consists of a screening period of approximately 8 weeks, a treatment period of 48 weeks, and a safety follow-up period of 2 weeks. A schedule of assessment of all study procedures is provided in Table 1.

Concomitant use of riluzole is permitted when the doses and regimens will remain unchanged from the day of evaluation of ALSFRS-R at the screening visit through the end-of-treatment (EOT) or early termination (ET). Although dose reduction, dose interruption, or discontinuation due to the onset of AEs, progression of dysphagia, or gastrostomy while on oral edaravone 105 mg are allowed, it is prohibited to initiate the use of riluzole. Subjects who initiate riluzole therapy de-novo during the treatment period will be discontinued from the study. The use of AMX0035 will be allowed for patients in the event that it becomes commercially available via prescription in their respective country. AMX0035 should be taken at least 1 hour after MT-1186.

EOT assessments will occur at Week 48 (Visit 15). For subjects who decide to enroll into the extension study, the Week 48 study procedures will be used as the screening/entry criteria.

For subjects who complete the double-blind treatment period and who do not enroll into the extension study, a safety follow-up telephone visit will occur at Week 50 (Visit 16). If a subject enrolls into the extension study, the safety follow-up telephone visit does not need to be conducted.

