#### 11.5 Permitted Concomitant Medications

Concomitant use of riluzole will be permitted when the doses and regimens remain unchanged from the day of evaluation of ALSFRS-R at the screening visit through the EOT/ET. Although dose reduction, dose interruption, or discontinuation due to the onset of AEs, progression of dysphagia, is allowed, it is prohibited to newly start the use of riluzole. New or additional use of AMX0035 will be allowed for patients in the event that it becomes commercially available via prescription in their respective country. AMX0035 should be taken at least 1 hour after MT-1186. Use of riluzole and AMX0035 will be recorded in the CRF when these medications are used for patients.

For subjects who take a supplemental vitamin B6, it is recommended to take the smallest feasible therapeutic dose at bedtime.

COVID-19 and other vaccines that have received emergency use authorization or approval are allowed. At a minimum, the following must be documented in the concomitant medication section of the eCRF: the type of vaccine, the manufacturer of the vaccine, and the date(s) the subject receives the vaccinations.

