# 17.4.3.3 Prior and Concomitant Medications

Prior medication is any medication taken within 3 months prior to screening. Concomitant medication is defined as any medication, other than study drug, which is taken during the study from screening period, including prescription, herbal and over-the-counter medications. Prior and concomitant medications except for riluzole will be summarized by Anatomical Therapeutic Chemical (ATC) level 2 categories and preferred name.

All concomitant medication will be coded using the WHO DD and ATC system. Each medication will be classified as prior medication if it is stopped prior to the first dose of study drug, or as concomitant medication if it is ongoing at the time of the first dose of study drug or is started after the first dose of study drug. Prior and concomitant medications except for riluzole will be summarized by treatment group by ATC level 2 categories and preferred name.

Riluzole and AMX0035 will be summarized separately.

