3.2. Study Estimands

3.2.1. Primary Estimand

As pre-defined in the protocol (V5.0), if more than a few death events ($\geq 5\%$ death percentage for all randomized subjects, e.g., ≥ 19 death events) are observed in this study, an alternative primary estimand as well as primary endpoint will be used to incorporate death cases as Intercurrent Events (ICE). It was confirmed that the threshold of 19 death cases was crossed in the blinded data review meeting and therefore, the following back-up estimand will be used with CAFS being the primary endpoint.

The primary estimand construction elements are:

- Treatment of interest: The initially randomized treatment – Group 1 edaravone daily to be compared with Group 2 edaravone on/off during 48-week period.
- Population: Subjects with ALS as defined in the analysis set.
- Variable: CAFS score at Week 48.
- ICEs handling strategy
 - ICE1 – Additional/new AMX0035 treatment during the 48-week double-blind treatment period will be handled using treatment policy strategy.
 - ICE2 – Early discontinuation during the 48-week double-blind treatment period will be handled using hypothetical strategy.
 - ICE3 – Death will be handled within CAFS score derivation using composite variable strategy.
- Population-level summary: Mean difference in the variable (as specified above) between the 2 randomized groups – Group 1 edaravone daily vs Group 2 edaravone on/off.

The treatment effect will be attributed regardless of the use of additional/new AMX0035 treatment (ICE1) and as if early discontinuation events did not occur (ICE2), accounting for Death event (ICE3).

Note: If death after early discontinuation (ICE2) was occurred, the death event will be included.

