8.4.1.2. Demographic and Other Baseline Characteristics

8.4.1.2.1. Demographics:

Continuous: age, height, weight, Body Mass Index (BMI);

Categorical: age categorized as ≤ 64 years versus ≥ 65 years, and ≤ 19 , 20–29, 30–39, 40–49,

50–59, 60–69, \geq 70, gender, race, ethnicity, country and region defined as America- AM, Europe -EU and Asia Pacific - AP

- BMI will be calculated as weight at screening (kg) / {height at screening (m)}² and reported to 1dp.

Table 2: Demographic and Baseline Characteristics

Category	Item	Type of Data	Definition/Breakdown
Demography	Gender	Binary	Male, Female
	Race	Categorized	
 1. White 2. Black or African American 3. Asian – Japanese 4. Asian - Not Japanese 5. American Indian or Alaska Native 6. Native Hawaiian or Pacific Islander 7. Not Reported 8. Other
	Age (year)	Continuous	
		Categorized	\leq 19, 20–29, 30–39, 40–49, 50–59, 60–69, \geq 70
		Categorized (binary)	<65 , ≥ 65
	Height (cm)	Continuous	
	Body weight (kg)	Continuous	
	BMI	Continuous	Weight at screening (kg) / {height at screening (m)} ²
	Country	Categorized	United States, Canada, Germany, Italy, Switzerland, Japan, South Korea
	Region	Categorized	
 1. America-AM 2. Europe -EU 3. Asia Pacific - AP
	Ethnicity	Categorized	
 1. Hispanic or Latino 2. Not Hispanic or Latino 3. Not Reported 4. Unknown

8.4.1.2.2. ALS History:

Continuous:

- (1) Disease Duration from Onset of Symptoms (years) and from ALS Diagnosis (years),
- (2) ALSFRS-R score at screening,
- (3) ALSFRS-R at Baseline,

Categorical:

- (1) ALSFRS-R Deterioration Rate of (-1,-2) or (-3,-4),
- (2) Disease duration from Onset of Symptoms categorized at <1 year vs \geq 1 year and from Onset of ALS Diagnosis categorized at <1 year vs \geq 1 year,
- (3) Initial symptom categorized as 'Bulbar onset' or 'Limb onset',
- (4) ALS Diagnosis categorized 'Sporadic' or 'Familial',
- (5) Categorical El Escorial revised Diagnostic,
- (6) Concomitant use of riluzole 'Present' or 'Absent',
- (7) Previous use of AMX0035 'Present' or 'Absent',
- (8) Concomitant use of AMX0035 'Present' or 'Absent',

Table 3 : ALS History Parameters

Category	Item	Type of Data	Definition/Breakdown
ALS Disease History	Disease duration from Onset of Symptoms to Screening (year)	Continuous	(Date of Screening - Date of Onset of Symptoms*)/365.25
	Categorized (binary)	< 1 year, \geq 1 year	

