8.4.1.4. Prior and Concomitant Medication

Definition of prior medications and concomitant medications in the protocol

At screening, subjects will be asked what medications (including riluzole) they have taken during the last 3 months prior to screening visit and will be recorded in the subject's source documents and eCRF as prior medication.

Concomitant medication is defined as any medication, other than the study drug, which is taken from screening up to week 48 Visit, including prescription, herbal and over-the-counter medications. All concomitant medications taken while the subject is participating in the study will be recorded in the eCRF.

All medications will be classified using the Anatomical Therapeutic Chemical (ATC) classification codes and preferred drug names from the World Health Organization Drug Dictionary (WHO-DD, version from September 2022).

Rules to determine prior medications and concomitant medications

Medications with a stop date before the first date of study drug dosing will be considered prior medications. Medications with start date or stop date on or after the first date of study drug dosing or ongoing up to week 48 will be considered concomitant medications. .

If the medication start date is incomplete, then it will be imputed as follows for the purpose of determining concomitant use:

- If the start date is completely missing, the start date will be equal to the first dose date. However, if the stop date is not missing and is before the first dose date, then the stop date will be used instead.
- If the start day is missing, the first day of the month will be used.
- If the start day and month are missing, then the first day of the first month (January) will be used.

If the medication stop date is partial, then it will be imputed as follows for the purpose of determining concomitant use:

- If the stop date is completely missing and the medication is not ongoing, the stop date will be equal to the last dose date or date of completion/withdrawal, whichever is the latest.
- If the stop day is missing, the last day of the month will be used.
- If the stop day and month are missing, then the last day of the last month (December) will be used.

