9.4. Subgroup analysis

The following subgroups will be analyzed for the key and the other secondary endpoints. For the continuous endpoints using MMRM (Change of %SVC, ALSAQ40 total score and ALSFRS-R total score), the model specified in section 9.2.1.1 will include additional fixed factor for the subgroup variable, the subgroup by treatment interaction as well as the subgroup by treatment by visit interaction. The influence of each subgroup factor will be investigated using the p-values for the interaction terms.

For the time to death, tracheostomy, or permanent assisted mechanical ventilation then the same Cox proportional hazard regression model will be used while adding the subgroup variable as well as the subgroup by treatment interaction. The influence of each subgroup factor will be investigated using the p-values for the interaction terms.

In addition, forest plot depicting the treatment effect and 95% CI for all subgroups will be displayed for change of ALSFRS-R total score and the time to death, tracheostomy, or permanent assisted mechanical ventilation.

Note: In some subgroup analyses, some factor will be statistically adjusted (e.g., in the country subgroup analysis, the Region factor will be removed).

- Gender (Female; Male)
- Race (White; Black; Asian; Other)
- Age (≥ 65 years old; < 65 years old)
- Region (North America; Europe; Asia)
- Body Weight (\geq Median; $<$ Median)
- BMI (\geq Median; $<$ Median)
- Country (United States; Canada; Germany; Italy; Switzerland; Japan; South Korea)
- Ethnicity (Hispanic or Latino; Other)
- Disease duration from onset of symptoms (< 1 year; ≥ 1 year)
- Disease duration from onset of diagnosis (< 1 year; ≥ 1 year)
- ALSFRS-R score at baseline (\geq Median; $<$ Median)
- ALSFRS deterioration strata for randomization (-1, -2; -3, -4)
- Initial symptom (Bulbar; Limb)
- ALS diagnosis (Sporadic; Familial)
- El Escorial revised Airlie House Diagnostic Criteria (Definite; Probable ALS)
- Concomitant use of riluzole (Present; Absent)
- Concomitant use of AMX0035 (Present; Absent)
- %FVC at baseline ($\geq 80\%$; $< 80\%$)
- %SVC at baseline ($\geq 80\%$; $< 80\%$)

- [REDACTED] at baseline (\geq Median; $<$ Median)
- [REDACTED] at baseline (\geq Median; $<$ Median)
- [REDACTED] at baseline (\geq Median; $<$ Median)
- [REDACTED] at baseline (\geq Median; $<$ Median)

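### SAP 9.4 splits subjects by AMX0035 use that may begin after randomisation, so that subgroup's treatment effects and interaction p-value lack the protection of randomisation and can be biased.

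*SAP*

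**What the plan says.** SAP 9.4 includes "Concomitant use of AMX0035 (Present; Absent" among its subgroups. For each subgroup the MMRM endpoints (%SVC, ALSAQ40, ALSFRS-R) and the Cox model for death, tracheostomy or permanent ventilation gain subgroup and interaction terms. The factor's influence is judged by interaction p-values. Forest plots follow for ALSFRS-R and the composite event.

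SAP 8.4.1.4 defines concomitant drugs as "Medications with start date or stop date on or after the first date of study drug dosing or ongoing up to week 48". Protocol 17.4.3.3 agrees, classing a drug "as concomitant medication if it is ongoing at the time of the first dose of study drug or is started after the first dose".

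In-trial starts are permitted. Protocol 11.5 says "New or additional use of AMX0035 will be allowed for patients in the event that it becomes commercially available", and Protocol 8.1 has a similar sentence. SAP 3.2.1 makes the same use an intercurrent event: "Additional/new AMX0035 treatment during the 48-week double-blind treatment period will be handled using treatment policy strategy".

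Table 3, in the ALS history part of SAP 8.4.1.2, lists "Previous use of AMX0035" separately from concomitant use. It gives no rule that fixes either item at baseline.

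**The concern.** A subgroup fixed before randomisation keeps the arms comparable within each level. A subgroup that subjects can enter later does not. Starting AMX0035 may depend on how a subject is declining, and decline is what the regimen is meant to change. Users in one arm may then differ in prognosis from users in the other, and so may non-users.

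SAP 9.4 applies no safeguard. ALSFRS-R, %FVC, %SVC and the redacted items on the same list are stated to be at baseline; AMX0035 is not. Riluzole also lacks that label, but its case differs because "it is prohibited to initiate the use of riluzole" during the trial, so concomitant riluzole is in effect a baseline factor.

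At stake is the reading of one forest-plot row and one interaction p-value per endpoint. 'Present' would mix subjects already on AMX0035 at first dose, a legitimate baseline group, with subjects who started later.

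**Working it through.** **The plan's own figure.** SAP 4.2 gives 190 per group, 30% dropout, a difference of 2.6, SD 7, two-sided 5% and 85.5% power. Completers per arm are 190 × 0.7 = 133. The noncentral t-test with 133 per arm gives 85.5%, so the figure is reproduced. The documents give no figure for the AMX0035 subgroup.

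**Simulation set-up.** There are 133 subjects per arm and 4,000 trials per scenario. The Week 48 change is y = 2.6·t + 7·e, where t = 1 for daily dosing and e is standard normal. Everyone has the same effect, so there is no true interaction, and AMX0035 itself has no effect.

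Assumptions that are not in the documents:
- The standardised early change is 0.7·e + √(1 − 0.49)·u + (2.6/7)·t, with u standard normal. It thus correlates 0.7 with Week 48 and carries the full treatment effect.
- logit P(start) = logit(base uptake) − slope × early change, so worse decline raises uptake.

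**Same uptake mechanism in both arms:**

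| Base uptake | Slope per SD | Absent | Present | Interaction rejected |
|---|---|---|---|---|
| 10% | 0 | 2.60 | 2.67 | 4.8% |
| 10% | 1 | 2.46 | 2.32 | 4.9% |
| 10% | 2 | 2.22 | 1.81 | 4.2% |
| 20% | 0 | 2.60 | 2.61 | 4.7% |
| 20% | 1 | 2.40 | 2.34 | 5.2% |
| 20% | 2 | 2.12 | 1.86 | 5.0% |
| 40% | 0 | 2.61 | 2.58 | 4.7% |
| 40% | 1 | 2.33 | 2.32 | 5.2% |
| 40% | 2 | 2.00 | 1.89 | 4.2% |

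When uptake ignores decline (slope 0), the truth is recovered. Otherwise both estimates shrink. The largest loss is (2.60 − 1.81)/2.60 = 30%. The interaction test stays near 5%. With no regimen effect and a shared mechanism, both differences are about 0 and rejection is about 5%, so there is no bias.

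**Mechanism differing by arm**, true difference 2.6, ranges over the three base uptakes:

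| Slope, on/off vs daily | Absent | Present | Interaction rejected |
|---|---|---|---|
| 1 vs 0.5 | 1.75–2.23 | 3.53–4.21 | 11.1–17.4% |
| 1 vs 0 | 0.90–2.02 | 4.98–6.44 | 37.5–66.3% |
| 2 vs 1 | 1.41–1.76 | 3.23–3.73 | 12.3–19.3% |

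Here a non-existent interaction is found too often. This also happens with no regimen effect (11.6% to 65.5%).

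**Time to event.** The control event rate is 10% by Week 48, from the 90% survival in SAP 4.2. Starts are assumed uniform over 48 weeks and AMX0035 is given no effect. Among controls, the event-rate ratio of users to never-users is 0.37 to 0.49, purely because users must be event-free until they start. The treatment hazard ratio within subgroups is 0.68 to 0.71 when the truth is 0.70, and about 0.30 to 0.31 when the truth is 0.30.

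**The case against.** The strongest objection is that nothing in the documents points to a false interaction. Subjects and site staff are blinded (Protocol 14.5) and both arms receive edaravone, so an uptake mechanism that differs by arm is not the expected case. With a shared mechanism the interaction test behaves. This stands: a reader might infer that the test is biased as planned, and the documents do not support that.

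A reader might also infer that guaranteed event-free time distorts the survival subgroup results. It distorts users against non-users, but 9.4 reports the regimen effect within each level, and that hardly moves.

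Uptake is also gated by country and calendar date, since "The use of AMX0035 will be allowed for patients in the event that it becomes commercially available via prescription in their respective country". This weakens the link with progression but does not remove it.

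The shift is modest beside the noise. If 40% of 133 completers per arm are users (53 users, 80 non-users), the standard errors are 7·√(2/53) = 1.36 and 7·√(2/80) = 1.11. The largest shifts at 40% base uptake are 0.71 and 0.60, about half a standard error each.

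Finally, ICE1 has its own analyses: treatment policy in the primary estimand, a hypothetical strategy in the secondary, and counts by arm (SAP 9.1.2). These deal with AMX0035 for the primary endpoint. They do not repair a subgroup in 9.4 that conditions on the same event.

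**Conclusion.** The point holds in a limited form. As written, the AMX0035 subgroup includes use begun after randomisation, so its treatment effects and interaction p-values can be biased. Bias requires either uptake related to progression together with a regimen effect, or uptake that depends on progression differently by arm. The documents establish neither, so the size and direction in this trial are unknown. Under a shared mechanism, estimates of about 1.8 to 2.5 against a true 2.6 are an illustration that rests on assumed uptake, slope and correlation.

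Nothing here reaches the main result. Section 9.4 covers key and other secondary endpoints and lies outside the fixed sequence in SAP 7.3, and the primary CAFS test and its type I error are unaffected. This is a cheap improvement of low severity.

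**What to change.** In SAP 9.4, replace the item with: *AMX0035 ongoing at first dose of study drug (Present; Absent)*, derived from the medication start and stop dates on which SAP 8.4.1.4 already relies. Report in-trial starts descriptively and through the existing ICE1 analyses, with no interaction p-value.

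Two tempting substitutes should be avoided. 'Previous use' is not a baseline-use variable if it follows the prior-medication rule in 8.4.1.4: it would pick out subjects who had stopped before first dose and miss those still taking the drug. A time-dependent AMX0035 term in the Cox model removes the guaranteed event-free time, but its interaction with treatment would still condition on a post-randomisation event.

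The cost is one line. SAP section 2 allows updates before final database lock and otherwise calls for a justified deviation in the study report. The drawback is that few subjects may be on AMX0035 at first dose; if so, show that group descriptively only.

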9.5. Nerve conduction Test

Absolute value and change from baseline in the CMAP, MUNIX and MUSIX in each different muscle (Abductor Pollicis Brevis, Abductor Digiti Minimi, Tibialis Anterior) in both left and right sides will be analyzed by each visit using descriptive statistics for continues variables. CMAP, MUNIX and MUSIX and the other parameters including proximal amplitude in the motor nerve test, distal amplitude and conduction velocity in the sensory nerve test will be listed.

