# 12.3.3 Nerve Conduction Testing/Electrophysiologic Assessment

At study sites selected by the Sponsor, and for subjects who consent, the Investigator (or subinvestigator) will measure the parameters (%CMAP, MUNIX, SNAP, and SNCV) using the nerve conduction test as described in Table 1. The evaluation results, together with the dates of evaluation, will be recorded in the eCRF. The methods and details will be outlined in the Study Reference Manual.

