# 17.4 Statistical Analyses

#### 17.4.1 General Considerations

The statistical analysis will be performed using SAS® Version 9.4 or higher.

In general, continuous variables will be summarized descriptively using the number of observations (n), mean, SD, median, minimum, and maximum. Categorical variables will be summarized using frequency counts and percentages.

Unless otherwise specified, all statistical tests will be done as 2-sided at the 5% significance level. Point estimates of treatment differences will be accompanied with 2-sided 95% CIs where applicable.

Statistical summaries will be presented for the changes from baseline to each visit for the primary, secondary (key and other), and exploratory endpoints that are applicable.

All individual subject data will be listed.

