#### 17.4.5.10 Exploratory Endpoint Analyses

Change from baseline in %CMAP, MUNIX, SNAP, and SNCV will be summarized by treatment group, where appropriate using descriptive statistics. The exploratory biomarker parameters at each visit will be appropriately summarized by treatment group. The details will be included into the SAP.

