2. INTRODUCTION

This statistical analysis plan (SAP) is based on the final global protocol (v5.0) dated 22-Sep-2022. The plan covers statistical analysis, tabulations and listings of the study data to evaluate and compare the efficacy, safety and tolerability of Oral edaravone 105 mg administered once daily to Oral edaravone 105 mg administered in cycles of ‘on/off’¹ in subjects with ALS over 48 weeks. The structure and content of this SAP provides sufficient details to meet the requirements identified by the FDA and International Conference on Harmonization of Technical Requirements for Registration of Pharmaceuticals for Human Use (ICH): E9 Guidance on Statistical Principles in Clinical Trials. All work planned and reported for this SAP will follow internationally accepted guidelines, published by the American Statistical Association, and the Royal Statistical Society, for statistical practice.

¹ 14 days, followed by placebo for 14 days and subsequently, repeat oral edaravone 105 mg administered for 10 days followed by placebo for 18 days

Statistical Analysis Plan
Protocol No. MT-1186-A02

Mitsubishi Tanabe Pharma America, Inc.

The following documents were reviewed in preparation of this SAP:

- Clinical Study Protocol MT-1186-A02 Version 5.0
- Case report form (CRF) for MT-1186-A02
- Standard Operating Procedure (SOP) GLB-BST-SOP002 for Statistical Analysis Plan
- ICH E9 Guidance on Statistical Principles for Clinical Trials.
- ICH E3 Structure and Content of Clinical Study Reports (CSRs)
- ICH E14 (may, 2005) clinical evaluation of QT/QTC interval prolongation

Any statistical analysis details described in this document supersede the description of statistical analysis in the protocol. In case of major differences, e.g. changes in the analysis related to the primary endpoint, a protocol amendment will be considered. The SAP may be updated during the study conduct and will be finalized before final database lock. Any deviations from the planned analysis will be described and justified in the CSR.

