3.3.5. Exploratory Endpoint(s)

Exploratory endpoints will include the following

- Nerve conduction test (%CMAP, MUNIX, SNAP and SNCV) at selected sites
- [REDACTED]

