6.1.3. Safety Analysis Set (SAF)

The SAF is defined as all randomized subjects who received at least 1 dose of study medication. Subjects will be grouped and analyzed based on the actual treatment received. Safety endpoints will be analyzed using the SAF by treatment group.

6.1.4. Exploratory biomarker Analysis Set (Ex-biomarker Set):

The Ex-biomarker Set is defined as all randomized subjects who received at least 1 dose of study medication and had any biomarker data collected after dosing. Biomarker endpoints will be analyzed using the Ex-biomarker Set

6.1.5. Exploratory Nerve conduction test Analysis Set (Ex-nerve Set):

The Ex-nerve Set is defined as all randomized subjects who received at least 1 dose of study medication and had any %CMAP, MUNIX, SNAP, and/or SNCV analysis after dosing. Nerve conduction test endpoints will be analyzed using the Ex-nerve Set.

6.1.6. Pharmacokinetic (PK) Population:

PK population includes all subjects who receive at least 1 dose of oral edaravone and who have at least 1 post-dose value for plasma concentration without important protocol deviations which may affect the PK of oral edaravone.

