8.4.4.1. Nerve conduction test

The Investigator (or sub-investigator) will measure the parameters (CMAP, MUNIX and MUSIX) using the nerve conduction test as described in Table 1 at selected sites. The evaluation results, together with the dates of evaluation, will be recorded in the eCRF. The methods and details will be outlined in the EMG/NCS procedure document.

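### SAP 9.5 only lists the sensory nerve endpoints (SNAP, SNCV), although the protocol plans by-arm summaries of their change from baseline, and SAP Section 11 does not declare the change

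*SAP*

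**What the plan says.** **Protocol.** Section 12.3.3 states that the investigator "will measure the parameters (%CMAP, MUNIX, SNAP, and SNCV) using the nerve conduction test". Section 17.4.5.10 gives the analysis: "Change from baseline in %CMAP, MUNIX, SNAP, and SNCV will be summarized by treatment group", using descriptive statistics where appropriate, with details left to the SAP. The synopsis says the same. Section 17.4.1 sets a general rule: "Statistical summaries will be presented for the changes from baseline to each visit for the primary, secondary (key and other), and exploratory endpoints", limited to those endpoints for which it is applicable.

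**SAP, where SNAP and SNCV are kept.** They appear in the exploratory objective (3.1.3), in the exploratory endpoints (3.3.5: "Nerve conduction test (%CMAP, MUNIX, SNAP and SNCV) at selected sites"), and in the Ex-nerve Set (6.1.5), which admits subjects who "had any %CMAP, MUNIX, SNAP, and/or SNCV analysis after dosing". A Table 1 footnote also names them among the parameters measured.

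**SAP, where they drop out.** Section 8.4.4.1 says the investigator "will measure the parameters (CMAP, MUNIX and MUSIX) using the nerve conduction test". Section 9.5 applies descriptive statistics to those three only. For the sensory test it says that "distal amplitude and conduction velocity in the sensory nerve test will be listed".

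**Precedence and declared changes.** SAP Section 2 states: "Any statistical analysis details described in this document supersede the description of statistical analysis in the protocol". Section 11 lists two changes from the protocol, the dropped physical-examination summary and the revised FAS definition. Neither concerns nerve conduction.

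**The concern.** Two endpoints that the protocol names for a by-arm summary are reduced to subject-level listings without a stated reason, while MUSIX, which the protocol does not mention, gains a summary. Because the SAP overrides the protocol's statistical text, the omission takes effect.

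CMAP and MUNIX are motor measures and are expected to fall as ALS progresses, whatever the drug does. Protocol 6.1 describes ALS as leaving sensation intact. On that description, SNAP and SNCV are the electrophysiological endpoints that disease progression should not move, so a difference between arms would be easier to interpret. Protocol 6.1.1.1 reports sciatic nerve vacuolation and atrophy, among other findings, in dogs at 300 mg/kg, and the trial compares two regimens with very different numbers of active-dose days. What is at stake is the only electrophysiological sensory part of the neurotoxicity comparison.

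**Working it through.** The plan gives no figure to reproduce for this point. The check compares the texts and makes two short counts.

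**1. The four protocol measures followed through the SAP**

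| Measure | Protocol 17.4.5.10 | SAP 3.3.5 and 6.1.5 | SAP 8.4.4.1 | SAP 9.5 |
|---|---|---|---|---|
| CMAP (%CMAP in the protocol) | summarise | named | named | descriptive statistics |
| MUNIX | summarise | named | named | descriptive statistics |
| SNAP | summarise | named | absent | listing only |
| SNCV | summarise | named | absent | listing only |
| MUSIX | not mentioned | not mentioned | named | descriptive statistics |

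SAP 9.5 does not use the labels SNAP and SNCV. Reading its sensory distal amplitude as SNAP and its sensory conduction velocity as SNCV is an inference. On any other reading, 9.5 contains nothing for SNAP and SNCV, which would be worse.

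**2. Internal consistency.** Under 6.1.5, SNAP or SNCV data alone can place a subject in the Ex-nerve Set, on which nerve-conduction endpoints are to be analysed. Section 9.5 then summarises neither measure. Section 8.4.4.1 refers to Table 1, whose footnote says both are measured.

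**3. Summaries lost.** Protocol Table 1 schedules the nerve conduction test at baseline and Weeks 12, 24 and 48, which gives three post-baseline visits.

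2 measures x 3 visits = 6 by-arm change-from-baseline summaries per nerve and side tested.

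This count combines 17.4.5.10 (which measures), 17.4.1 (each visit) and Table 1 (which visits). The documents do not say how many sensory nerves are tested.

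**4. Active-dose days over 12 cycles** (Protocol 8.1)

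- Daily: 28 x 12 = 336.
- On/off: 14 + 11 x 10 = 124.
- Ratio: 336 / 124 = 2.71.

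**5. What is still summarised.** SAP 9.3.1.1 covers numbness, unsteadiness and vibratory sensation, and SAP 9.3.1 covers the peripheral neuropathy SMQ. The SMQ list in SAP Appendix 2 includes muscular weakness, muscle atrophy and gait disturbance, which ALS itself can produce. Muscular weakness was reported in 21.1% of patients in the earlier open-label oral study (Protocol 6.1.1.2). Overall SMQ incidence is therefore open to confounding by the disease.

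**The case against.** **The protocol delegated the detail.** Section 17.4.5.10 is qualified and leaves details to the SAP, and 17.4.1 covers only applicable endpoints. The parallel with physical examinations is inexact, because that protocol text was unconditional. This stands as far as it goes: the SAP may settle the form of the summary. It does not explain why two named endpoints have none while an unnamed one gains one, and the SAP does not say a summary would be inappropriate.

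**SAP 9.2.1 may already cover it.** That section promises by-arm summaries of continuous efficacy endpoints, and nerve conduction sits under an efficacy exploratory heading. But 9.5 is the specific text, and it separates what is analysed from what is listed. If 9.2.1 did apply, 9.5 would contradict it and still need correcting.

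**The safety reading is not the protocol's.** This stands. The protocol places these tests under exploratory efficacy. The claim that progression should not move SNAP or SNCV is inferred from a clinical description. The dog findings are not described as sensory only, so the motor measures may bear on them too. The dose is also far from the trial dose: at an assumed body weight of 50 to 100 kg, 105 mg is 2.1 to 1.05 mg/kg, and 300 mg/kg is about 143 to 286 times that, without adjustment for exposure. The ratio of 2.71 describes dosing days, not an effect on nerves.

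**Other coverage is substantial.** This also stands. The SMQ list includes abnormal nerve conduction studies and peripheral sensory neuropathy as preferred terms, so an abnormality reported as an adverse event would be tabulated. The listed values remain available. Neither gives a by-arm comparison of the measurements themselves.

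**Conclusion.** The concern holds. The SAP omits the by-arm summaries of SNAP and SNCV that the protocol plans, contradicts its own endpoint list and analysis-set definition, and does not record the change in Section 11. The size is two of four named endpoints, or six change-from-baseline summaries per nerve and side.

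The consequence is limited. The measures are exploratory, descriptive, outside the testing hierarchy, and collected at selected sites from consenting subjects. The documents do not give the substudy size, so nothing can be said about precision. The neurotoxicity comparison is weakened, not removed. This should be corrected, but it does not threaten the trial's main conclusions.

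The conclusion assumes that the sensory amplitude and velocity in 9.5 are SNAP and SNCV, and that the specific wording of 9.5 prevails over the general sentence in 9.2.1.

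**What to change.** 1. In SAP 9.5, summarise value and change from baseline in SNAP amplitude and SNCV at Weeks 12, 24 and 48 by treatment group on the Ex-nerve Set, with the same descriptive statistics as CMAP and MUNIX. State the by-group presentation explicitly, since 9.5 does not say it even for the motor measures.
2. In SAP 8.4.4.1, add SNAP and SNCV so that it agrees with 3.3.5 and 6.1.5, and state that MUSIX is an addition to the protocol's list.
3. If listings only are intended, enter the change and its reason in Section 11, as was done for physical examinations.

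The cost is two descriptive tables, with rows for each nerve and side, from data already collected and already due to be listed, plus one line of text in 8.4.4.1. No new data are needed and no test or error rate is affected.
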